6.1.1.3 Adverse Events Expected due to Study Related Endpoints

Disease progression is an endpoint of this study. Disease progression should not be reported as an adverse event.

6.1.1.3.1 Deaths

For this protocol, overall survival is an efficacy endpoint. Deaths that occur during the protocol specified adverse event collection period (Section 6.1.4) that are attributed by the investigator solely to progression of AML should be recorded only on the Death eCRF and the Study Completion Form eCRF. All other deaths during the protocol specified

adverse event collection period, regardless of relationship to study drug, must be recorded on the Adverse Event eCRF and Death eCRF and immediately reported to the Sponsor (Section 6.1.5). All deaths occurring after adverse event collection period should be collected in Death eCRF.

Death should be considered an outcome and not a distinct event. The event or condition that caused or contributed to the fatal outcome should be recorded as the single medical concept on the Adverse Event eCRF. Generally, only one such event should be reported. The term "sudden death" should only be used for the occurrence of an abrupt and unexpected death due to presumed cardiac causes in a patient with or without pre-existing heart disease, within one hour of the onset of acute symptoms or, in the case of an unwitnessed death, within 24 hours after the patient was last seen alive and stable. If the cause of death is unknown and cannot be ascertained at the time of reporting, "unexplained death" should be recorded on the Adverse Event eCRF. If the cause of death later becomes available (e.g., after autopsy), "unexplained death" should be replaced by the established cause of death.

6.1.2 Adverse Event Severity

The investigator will rate the severity of each adverse event according to the National Cancer Institute Common Terminology Criteria for Adverse Events (NCI CTCAE Version 4.03). When applicable, once the diagnosis is confirmed the medical term should be reported for an event rather than the abnormal lab values as identified in CTCAE. If a reported adverse event increases in severity, the initial adverse event should be given final outcome date and a new adverse event must be reported to reflect the change in severity. If a reported adverse event increases in severity, the initial adverse event should be given final outcome date and a new adverse event must be reported to reflect the change in severity such that the dates on these AE's cannot overlap. For all reported serious adverse events that increase in severity, the supplemental eCRFs also need to be updated to reflect any changes due to the increase in severity.

For adverse events not captured by the Common Terminology Criteria, the following should be used:

- Grade 1** The adverse event is transient and easily tolerated by the subject (mild).
- Grade 2** The adverse event causes the subject discomfort and interrupts the subject's usual activities (moderate).
- Grade 3** The adverse event causes considerable interference with the subject's usual activities and may be incapacitating (moderate to severe).
- Grade 4** The adverse event is life-threatening requiring urgent intervention (severe).
- Grade 5** The adverse event resulted in death of the subject (severe).

6.1.3 Relationship to Study Drug

The investigator will use the following definitions to assess the relationship of the adverse event to the use of study drug:

- Reasonable Possibility** After consideration of factors including timing of the event, biologic plausibility, clinical judgement, and potential alternative causes, there is **sufficient** evidence (information) to suggest a causal relationship.
- No Reasonable Possibility** After consideration of factors including timing of the event, biologic plausibility, clinical judgement, and potential alternative causes, there is **insufficient** evidence (information) to suggest a causal relationship.

The Investigator will assess the relationship of each adverse event to venetoclax/placebo, and to LDAC. Some events may be reasonably related to more than one drug or to none. For causality assessments, events assessed as having a reasonable possibility of being related to the study drug will be considered "associated." Events assessed as having no reasonable possibility of being related to study drug will be considered "not associated." In addition, when the Investigator has not reported causality or deemed it not assessable, AbbVie will consider the event associated to study drug.

If an Investigator's opinion of no reasonable possibility of being related to study drug is given, an "Other" cause of event must be provided by the Investigator for the serious adverse event.

6.1.4 Adverse Event Collection Period

[figure not shown]
All protocol-related serious adverse events and nonserious adverse events must be collected from the signing of the study specific informed consent until study drug administration.

Serious and nonserious adverse events occurring after the study-specific informed consent is signed but prior to the initial dose of venetoclax/placebo, or LDAC will be collected only if they are considered by the Investigator to be causally related to the study-required procedures.

In addition, all serious and nonserious adverse events reported from the time of study drug administration until 30 days following discontinuation of study drug administration have elapsed will be collected, whether elicited or spontaneously reported by the subject.

Adverse event information will be collected as shown in [Figure 2](#).

Figure 2. Adverse Event Collection

* Only if considered by the Investigator to be causally related to study-required procedures.

6.1.5 Adverse Event Reporting

In the event of a serious adverse event, whether associated with study drug or not, the investigator will notify Clinical Pharmacovigilance within 24 hours of the site being made aware of the serious adverse event by entering the serious adverse event data into the electronic data capture (EDC) system. Serious adverse events that occur prior to the site having access to the RAVE[®] system or if RAVE is not operable should be documented on the SAE Non-CRF forms and emailed (preferred route) or faxed to Clinical Pharmacovigilance within 24 hours of being made aware of the serious adverse event.

Email:	[REDACTED]
FAX to	[REDACTED]

For safety concerns, contact the Oncology Safety Management Team at:

Oncology Safety Management
[REDACTED]
AbbVie
[name]
[name]

[REDACTED]

For any subject safety concerns, please contact the physician listed below:

AbbVie TA Medical Monitor:

In emergency situations involving study subjects when the AbbVie Medical Monitor is not available by phone, please contact the 24-hour AbbVie Medical Escalation Hotline where your call will be re-directed to a designated backup AbbVie SDP:

Phone:	
---------------	---

The sponsor will be responsible for Suspected Unexpected Serious Adverse Reactions (SUSAR) reporting for the Investigational Medicinal Product (IMP) in accordance with Directive 2001/20/EC.

AbbVie will be responsible for Suspected Unexpected Serious Adverse Reactions (SUSAR) reporting for the Investigational Medicinal Product (IMP) in accordance with global and local guidelines and Appendix A of the Investigator Brochure will serve as the Reference Safety Information (RSI). The RSI in effect at the start of the DSUR reporting period serves as the RSI during the reporting period. For follow up reports, the RSI in place at the time of occurrence of the 'suspected' Serious Adverse Reaction will be used to assess expectedness.

In Japan, the principal investigator will provide documentation of all serious adverse events to the Director of the investigative site and the Sponsor.

6.1.6 Pregnancy

While not an adverse event, pregnancy in a study subject must be reported to AbbVie within 1 working day of the site becoming aware of the pregnancy. Subjects who become pregnant during the study must be discontinued. If a pregnancy occurs in a study subject or in the partner of a study subject, information regarding the pregnancy and the outcome will be collected.

In the event of pregnancy occurring in a subject's partner during the study, written informed consent from the partner must be obtained prior to collection of any such information. A separate consent will be provided by AbbVie for this purpose. Pregnancy in a subject's partner will be collected from the date of the first dose through 180 days following the last dose of study drug.

The pregnancy outcome of an elective or spontaneous abortion, stillbirth or congenital anomaly is considered a SAE and must be reported to AbbVie within 24 hours of the site becoming aware of the event.

6.1.7 Toxicity Management

Management of Cytopenias, Infections, and Other Adverse Events

Myelosuppression and the related adverse events (thrombocytopenia, anemia, neutropenia, and febrile neutropenia) are common in both treated and untreated subjects with AML. Subjects with baseline neutropenia or have significant bone marrow involvement may be particularly at high risk. If a participant achieves a CRi or a morphologic leukemia free bone marrow, and has Grade 4 neutropenia or thrombocytopenia persisting beyond Day 28, venetoclax should be interrupted from Day 28 until ANC \geq 500 – 1000/ μ L and platelet count \geq 25 – 100 \times 10³/ μ L. Typically, if persistent AML remains in the bone marrow, concurrent cytopenias are thought to be attributable to the disease process of AML and continued treatment with venetoclax and

LDAC may continue on schedule. In subsequent cycles, if a subject with previous CR presents with new onset Grade 4 neutropenia or thrombocytopenia lasting more than one week, unless it is due to the underlying disease, venetoclax dosing may be interrupted until ANC recovery to $\geq 500 - 1000/\mu\text{L}$ and platelet count $\geq 25 - 100 \times 10^3/\mu\text{L}$ per investigator discretion in consultation with the AbbVie medical monitor. Venetoclax may be re-initiated at a lower dose, or discontinued if a minimal dose is not tolerable, per discussion with the AbbVie medical monitor.

Administration of venetoclax in subjects with lymphoproliferative disorders has been associated with clinically significant lymphopenia (B and T lymphocyte subtypes). Anti-infective prophylaxis for viral, fungal, bacterial or Pneumocystis infections are required for all subjects with ANC of $< 500/\mu\text{L}$. Institutional infectious organisms and their drug resistance patterns should primarily be considered and the choice of these agents should be based on regional guidelines or institutional standards. Potential for drug-drug interactions should be considered. Please refer to [Table 1](#), [Table 2](#), and [Appendix I](#) for a description of excluded and cautionary medications and implement dose reductions for venetoclax/placebo as necessary.

If a subject is continuing to respond based on the bone marrow assessment after Cycle 2 of treatment, but has persistent cytopenias (cytopenias that occur after Day 28 of a Cycle during Cycle 2 and beyond), venetoclax dose may be reduced as follows:

Table 7. Dose Reduction Guidelines for Management of Persistent Neutropenia or Thrombocytopenia

Venetoclax Dose/Duration	New Venetoclax Dose/Duration
600 mg daily \times 28 day cycles	600 mg daily \times 21 days with 7 day interruption
600 mg daily \times 21/28 day cycles	600 mg daily \times 14 days with 14 day interruption
600 mg daily \times 14/28 day cycles	400 mg daily \times 14 days with 14 day interruption

Cytopenias during Cycle 1 or 2 may be due to bone marrow involvement by AML and therefore dose reductions during Cycle 1 or 2 are not typically recommended. If an

investigator believes a particular patient would benefit from a dose reduction during Cycle 1 or 2, the investigator should discuss with the medical monitor.

If dose reductions or interruptions for events other than cytopenias or infections are thought to be necessary by the investigator, a discussion with the AbbVie medical monitor is required and may be approved upon consultation. Delays greater than 21 days must be discussed with the AbbVie medical monitor or a designee.

Standard Therapy: Low – Dose Cytarabine

In a recent international clinical trial, subjects receiving LDAC experienced the following treatment emergent CTCAE grade 3 or 4 adverse events at a rate of at least 10%: thrombocytopenia 35%, anemia 27%, febrile neutropenia 25%, disease progression 22%, neutropenia 20%, pneumonia 19%, general physical health deterioration 16%, and leukopenia 10%.³⁶ It is unknown whether the aforementioned adverse events are attributable to receiving treatment with LDAC or were attributable to the underlying health condition of AML. Complications of myelosuppression, including infections and bleeding, may be exacerbated by treatment with LDAC. During Cycle 2 and subsequent cycles, study treatments may be delayed at the discretion of the investigator, if the subject experiences myelosuppression associated complications, such as those described below:

- Febrile neutropenia (temperature $\geq 38.5^{\circ}\text{C}$ and ANC $< 1,000/\mu\text{L}$)
- Active viral, bacterial or fungal infection (i.e., requiring IV anti-infectives or extensive supportive care)
- Hemorrhage (gastrointestinal, genito-urinary, pulmonary with platelets $< 25,000/\mu\text{L}$ or any central nervous system hemorrhage)

Treatment with LDAC may be resumed once the above conditions have improved or have been stabilized with adequate treatment (anti-infective therapy, transfusions, or growth factors).

Myelosuppression caused by LDAC is reversible. Complete blood and platelet counts should be performed regularly, as clinically indicated and prior to each treatment cycle.

In the presence of myelosuppression or its complications, treatment with LDAC may be interrupted or supportive measures instituted.

LDAC dose reductions are not typically recommended. If a dose reduction is believed to be necessary a discussion with the AbbVie medical monitor is required.

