** If a narrow therapeutic index P-gp substrate must be used, it should be taken at least 6 hours before venetoclax.

Table 2. Dose Modifications for Venetoclax: Moderate and Strong CYP3A Inhibitor Use

Assigned Venetoclax Dose	Modified Dose if Co-Administered with a Moderate CYP3A or P-gp Inhibitor	Modified Dose if Co-Administered with a Strong CYP3A Inhibitor
100 mg	50 mg	10 mg
200 mg	100 mg	20 mg
400 mg	200 mg	50 mg
600 mg	300 mg	50 mg

Note: After discontinuation of the inhibitor, wait for 2 to 3 days before venetoclax dose is increased back to the previous dose level. Ramp-up is not required upon discontinuation of the inhibitor.

A sample list of excluded medications and cautionary medications that fall into the categories within this section of the protocol can be found in [Appendix I](#). It is not possible to produce a comprehensive list of medications that fall into these categories, so if in question, please refer to the appropriate local product label and/or FDA website: <http://www.fda.gov/Drugs/DevelopmentApprovalProcess/DevelopmentResources/DrugInteractionsLabeling/ucm080499.htm> and notify the AbbVie Medical Monitor and discuss the investigator's intended use of these medications with the subject in question and the investigator's plans to medically monitor the potential study subject.

Commonly used anti-infective agents for prophylaxis (including ciprofloxacin and azole anti-fungal medications) and calcium channel blockers (diltiazem and verapamil) have CYP3A inhibitory properties and dose reductions of venetoclax/placebo are required.

Steroid therapy during study participation should be limited to lower dose and short duration if medically indicated. Intrathecal chemotherapy or radiation therapy for CNS prophylaxis is not permitted during study participation.

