5.6.4.1 Dose Adjustments for Venetoclax Upon Co-Administration with Anti-Fungal Agents

Patients with AML are at high risk for febrile neutropenia and life threatening fungal infections. Azole agents, all of which are CYP3A inhibitors, are widely used in these patients for prophylaxis and treatment of invasive fungal infections. As venetoclax is predominantly metabolized by CYP3A, co-administration with antifungal agents which are strong or moderate CYP3A inhibitors will increase venetoclax exposures.

The effect of two strong CYP3A inhibitors (posaconazole and ketoconazole) on the pharmacokinetics of venetoclax was evaluated in two separate studies. Study M13-364 was conducted to evaluate the effect of ketoconazole given once daily on pharmacokinetics of single dose of venetoclax in 12 subjects with NHL³⁴ and a cohort of 12 untreated elderly AML subjects in Study M14-358 was enrolled to assess the effect of posaconazole given twice daily on exposures of venetoclax given once daily.³⁵ Furthermore, prior studies indicated venetoclax bioavailability to be dependent on both food and dose. To account for the effect of covariates such as food and dose non-linearity on the bioavailability of venetoclax, a population PK model was used to simulate exposures of venetoclax in presence of strong CYP3A inhibitors.

The ramp-up scheme for venetoclax when given alone is 100 mg on Day 1, 200 mg on Day 2, 400 mg on Day 3 and 600 mg QD from Day 4 onwards. To match the exposures (AUC) from these doses, venetoclax doses of 10 mg on Day 1, 20 mg on Day 2 and 50 mg QD from Day 3 onwards were chosen when co-administered with strong CYP3A

inhibitors to mitigate any possible risk for TLS and ensure safety. Predicted venetoclax exposures when administered alone and in presence of strong CYP3A inhibitors at the recommended dose reductions are shown in [Table 6](#).

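### With a strong CYP3A inhibitor, the third dose-reduction step in Table 7 leaves the nominal venetoclax dose unchanged at 700 mg per cycle

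*Protocol*

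**What the plan says.** Table 7 (Protocol 6.1.7) applies to subjects who are still responding in the marrow after Cycle 2 but have persistent cytopenias. It is a guideline: the dose may be reduced, not must be. It goes from 600 mg on 28 days to 600 mg on 21 days, then to 600 mg on 14 days, then to 400 mg on 14 days. The last two rows both specify "14 days with 14 day interruption". The table has no row or footnote for subjects on a CYP3A inhibitor.

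Table 2 (Protocol 5.2.3) converts an assigned dose when an inhibitor is used. Its column headed "Modified Dose if Co-Administered with a Strong CYP3A Inhibitor" gives 50 mg for 400 mg and 50 mg for 600 mg. The table is not confined to ramp-up. The text after it says that common anti-infective agents, azole anti-fungals among them, "have CYP3A inhibitory properties and dose reductions of venetoclax/placebo are required", and its note deals with what happens later: "After discontinuation of the inhibitor, wait for 2 to 3 days before venetoclax dose is increased back to the previous dose level".

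Section 5.6.4.1 explains the plateau. To match the exposures of the standard ramp-up, "venetoclax doses of 10 mg on Day 1, 20 mg on Day 2 and 50 mg QD from Day 3 onwards were chosen" for use with strong inhibitors. Section 6.1.7 refers the reader to Table 2 in the paragraph just before the one that introduces Table 7.

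**The concern.** The third step works only through the daily dose, and Table 2 removes that difference for a subject on a strong inhibitor. A site that follows both tables as written reaches the last rung of the ladder and gives the same tablets on the same days to a subject whose cytopenia has not resolved.

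The overlap is foreseeable. Section 6.1.7 states: "Anti-infective prophylaxis for viral, fungal, bacterial or Pneumocystis infections are required for all subjects with ANC of" below 500/µL. Section 5.6.4.1 describes azoles as widely used in AML, and Appendix I lists several of them (itraconazole, ketoconazole, posaconazole, voriconazole) as strong inhibitors. Others, such as fluconazole and isavuconazole, are listed as moderate, and the choice of agent is left to regional or institutional practice.

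The checks next to Table 7 are not aimed at this step. The required discussion with the medical monitor begins "If dose reductions or interruptions for events other than cytopenias or infections are thought to be necessary by the investigator", which leaves cytopenias out. The other trigger is a delay longer than 21 days, and the planned gap is shorter than that.

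**Working it through.** The documents state no per-cycle total, so there is no figure of the plan's own to reproduce. The check is a table look-up followed by multiplication.

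**Inputs**
- Schedules, from Table 7: 600 mg x 28, 600 mg x 21, 600 mg x 14 and 400 mg x 14 days per 28-day cycle.
- Conversions, from Table 2: 600 mg becomes 300 mg (moderate CYP3A or P-gp inhibitor) or 50 mg (strong); 400 mg becomes 200 mg (moderate) or 50 mg (strong).

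**Formula:** nominal mg per cycle = converted daily dose x dosing days. Change = (after - before) / before.

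| Table 7 position | No inhibitor | Moderate | Strong |
|---|---|---|---|
| Start | 600 x 28 = 16,800 | 300 x 28 = 8,400 | 50 x 28 = 1,400 |
| After step 1 | 600 x 21 = 12,600 (-25%) | 300 x 21 = 6,300 (-25%) | 50 x 21 = 1,050 (-25%) |
| After step 2 | 600 x 14 = 8,400 (-33%) | 300 x 14 = 4,200 (-33%) | 50 x 14 = 700 (-33%) |
| After step 3 | 400 x 14 = 5,600 (-33%) | 200 x 14 = 2,800 (-33%) | 50 x 14 = 700 (0%) |

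Only the strong-inhibitor column loses a step, and only the third.

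**Cross-checks**
- Section 5.6.4.1 agrees with the look-up: 50 mg from Day 3 onwards covers both the 400 mg day and the 600 mg days.
- Appendix I asks for at least a 4-fold reduction with a strong inhibitor, which sets ceilings of 600/4 = 150 mg and 400/4 = 100 mg. Table 2's 50 mg is a 12-fold and an 8-fold reduction, so it meets both. The two places do not conflict.
- The planned gap in steps 2 and 3 is 28 - 14 = 14 days, below the 21-day rule.

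**Exposure.** Nominal milligrams cannot be compared across inhibitor states. Section 5.6.4.1 says that bioavailability depends on food and on dose, and the predicted exposures of Table 6 are not in the text available here. If 50 mg with a strong inhibitor lies near the exposure of 400 mg alone, little of the intended reduction is lost; if it lies near that of 600 mg alone, more is lost.

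**The case against.** The best reply does not dispute the arithmetic. It says that little follows from it, and much of that stands.

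- **The plateau is deliberate.** The 50 mg dose was chosen from a population PK model. A reader might infer that the affected subject is over-exposed, or that harm has been shown. The documents do not support that: the subject may already be close to the exposure that the third step aims for. What remains is that a subject whose cytopenia persists at 50 mg x 14 days gets no change of regimen from a step listed as a reduction.
- **Other routes exist.** Section 5.2.3 sends questions about concomitant therapy to the medical monitor, both before Table 1 and after Table 2. Section 6.1.7 adds, for new Grade 4 cytopenia after CR: "Venetoclax may be re-initiated at a lower dose, or discontinued if a minimal dose is not tolerable". Interruption and discontinuation are also available, and 10 mg tablets are supplied. These routes are general. None of them mentions Table 7 or names a dose, but they are a real safeguard.
- **The group is narrower than the prophylaxis rule suggests.** Section 6.1.7 handles Grade 4 neutropenia by holding venetoclax until ANC recovers to 500-1000/µL. Subjects for whom prophylaxis is mandatory will therefore largely fall under those provisions rather than Table 7. This stands.
- **The null result is visible.** Whoever prescribes the step has to write 50 mg again. This stands too, and Table 7 is only permissive.
- **The two tables are linked.** One might infer that nothing connects them. In fact Section 6.1.7 cites Table 2 just before Table 7, and Table 2 has a 400 mg row. The mapping is given; the difficulty is its result.

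A reader might also infer that SAP 11.1, which counts adverse events leading to venetoclax/placebo reduction, would be distorted. Nothing shows that an unchanged dose would be recorded as a reduction, and the final analysis has already been done.

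**Conclusion.** The point holds for nominal dose. With a strong CYP3A inhibitor, step 3 of Table 7 is 700 mg to 700 mg per cycle (0%), against -33% with no inhibitor or a moderate one. Steps 1 and 2 are unaffected, so it would be wrong to say that the ladder as a whole fails for these subjects.

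The conclusion rests on one reading: that the 400 mg in Table 7 is an assigned dose to be converted by Table 2. That is the natural reading given the cross-reference.

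The effect on exposure and the number of subjects affected cannot be stated from the documents. Those concerned are still responding after Cycle 2, have persistent cytopenia, are already at 14 of 28 days, and take a strong inhibitor. Because the final analysis is complete, only subjects who remain on treatment under Section 5.4.1 could benefit from a change. No efficacy analysis depends on it. It is a low-priority safety clarification, worth making because a written safety step has no effect when followed and the correction is one note.

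**What to change.** Add one note under Table 7:

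> With a strong CYP3A inhibitor, the step from 600 mg to 400 mg (14/28 days) does not lower the dose, because Table 2 gives 50 mg for both. Do not use this step. Contact the medical monitor to decide on interruption, discontinuation, a change of concomitant agent, or a lower dose if the sponsor has set one from its population PK model.

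Two limits belong with it. First, no dose below 50 mg should be named without exposure predictions from the sponsor, because the documents give no basis for one. Second, changing to another agent and then giving 400 mg alone, or 200 mg with a moderate inhibitor, should not be presented as a reduction unless those predictions show lower exposure. The 50 mg dose was matched to the exposures of the 400 mg and 600 mg days, so a fall is not assured, and the Table 2 note covers only a return to the previous dose level.

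**Cost.** A protocol change needs IEC/IRB approval (Section 9.1) across about 125 sites, so the note should travel with other changes and not prompt an amendment alone. It adds a few medical-monitor calls. A change of anti-fungal agent may alter infection cover and has to be judged for each subject. A lower dose would need PK work by the sponsor and supply through the IRT before it could be offered. No extra subjects or visits are needed.
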